7. SAFETY ASSESSMENTS

The risk to Veterans who participate in this study is minimal. Nevertheless, research staff will be trained in the detection and investigation of adverse events during the conduct of study assessments or other interactions with participants.

Expected adverse experiences include:

- Counseling session or study procedures upsets participant
Criteria for management: Careful training of study staff and SBIRT-PM counselors will precede study initiation. If a participant complains about study procedures or counseling sessions, the complaint will be logged and will be brought to the attention of the mPIs. Depending on the nature of the complaint, mPIs will decide whether the complaint requires follow-up directly with the participant.
- Suicidal ideation detected by the PHQ-9 or by counseling
Criteria for management: item 9 in the PHQ-9 identifies potential suicidal ideation (the questions asks about “thoughts of being better off dead or of hurting yourself in some way”). It is collected at baseline and at 12- and 36-week follow-ups. Any positive response (response other than “none at all”) to this question will be further evaluated, as well as other expressions of suicidality to the research assistant or SBIRT-PM clinician. Positive responses will be evaluated by one of the mPIs, Site-PIs, or covering providers. The response to clinical emergencies will be delineated in the Service Use Agreements between the hub site and spoke for provision of SBIRT-PM. If the research team decides that the information must be reported, the person who spoke to the Veteran (clinician or research assistant) will contact the Site-PI from the relevant medical center, and if he or she is not available, the clinician designated by the spoke site for handling mental health crises at the sites. All VISN1 medical centers have emergency room facilities and a suicide prevention coordination team. If the participant’s situation precludes management by spoke personnel (e.g. the Veteran is not accessible to VA staff or the site PI), the Research Assistant will immediately consult with one of the mPIs about ways to handle the situation, including calling for a police safety check on the Veteran.

7.1 Specification of Safety Parameters

NA.

7.2 Methods and Timing for Assessing, Recording, and Analyzing Safety Parameters

Unanticipated problems will be recorded as they are discovered throughout the study. The Project Director will record all reportable events with start dates occurring any time after informed consent is obtained until the last day of study participation (approximately 36 weeks after baseline). At each study visit (Baseline, week 12, week 36), the study team will inquire about the occurrence of AE/SAEs since the last visit.

Our group completed a randomized controlled trial of 101 participants to a face-to-face version of SBIRT-PM or two control conditions in a very similar population to that

proposed in this application ([name] et al., 2018). There were no study-related adverse events in that study, and they are unlikely in this study as well.

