We will use the customized Resource Allocation Worksheet to estimate the costs of delivering SBIRT-PM from the perspective of the providers (i.e., both the VISN and hospital). Cost estimation for VA services used by Veterans during the 36-week study period will be assessed using national VA administrative databases. Data on service use at the individual patient level will come from the VA National Patient Care Database (NPCD), which includes information on all inpatient and outpatient encounters at VA facilities. Costs for these services will be computed using the VA Average Cost Database, developed by the Health Economics Resource Center (HERC). The Average Cost Database assigns an average cost to each inpatient admission and outpatient visit in VA. Costs are based on Current Procedure Terminology (CPT) codes and can be linked to unique records in the NPCD.

Costs for VA services used by Veterans during the 36-week study period will be assessed using national VA administrative databases. Data on VA service use at the individual patient level will come from the VA National Patient Care Database (NPCD),

which includes information on all inpatient and outpatient encounters at VA facilities. Costs for these services will be computed using the VA Average Cost Database, developed by the Health Economics Resource Center (HERC). The Average Cost Database assigns an average cost to each inpatient admission and outpatient visit in VA. Costs are based on Current Procedure Terminology (CPT) codes and can be linked to unique records in the NPCD. Costs incurred by VA for community care will be obtained from databases tracking payments to community providers.

Procedures to develop a new natural language processing (NLP) algorithm that identifies use of non-pharmacological pain management services

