After the initial session, the counselor will have up to three 20-minute, mutually scheduled phone counseling sessions with the Veteran (about once per month for 12 weeks) to check on the Veteran's status in achieving the goals of the plan, and to gauge his or her continued motivation to receive pain treatment and reduce risky substance use, as indicated. An additional call during the 12-32-week period is permissible to remotivate veterans to engage in available pain and substance use services in view of any healthcare system changes that occurred (see response to COVID-19 section below). These calls may be informed by information the counselor has obtained from the PACT providers or information in the electronic health record (e.g., seeing if a consult was placed, reviewing progress notes indicating engagement with services). Twelve weeks allows time for the Veteran to work with the counselor to resolve barriers to service engagement, consider other treatment options, and sustain motivation for and engagement in pain management and ancillary services. Moreover, meta-analyses and "dose-response" studies^{93,94} have suggested the benefit of several follow-up telephone sessions.

Coordination with PACT Providers. The counselor will communicate with the PACT nurse case manager and primary care provider, or other point-of-contact about recommended pain treatment referrals primarily via the electronic health record. SBIRT-PM counselors will write progress notes that indicate the SBIRT-PM encounter and outcome of each session, including asking the provider to consider placing a consult for the Veteran's preferred services or discussing the Veteran's interest in services at the Veterans next scheduled appointment. SBIRT-PM counselors cannot place consults for services directly; only PACT providers or other licensed professionals working with the Veterans at their VAs can do so.

SBIRT-PM Clinician Supervision.

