8. INTERVENTION DISCONTINUATION

This study will be stopped prior to its completion if: (1) the intervention is associated with adverse effects that call into question the safety of the intervention; (2) difficulty in study recruitment or retention will significantly impact the ability to evaluate the study endpoints; (3) any new information becomes available during the trial that necessitates stopping the trial; or (4) other situations occur that might warrant stopping the trial.

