Per NIH policy, because there is considerable data suggesting the importance of race, ethnicity and sex on the study outcomes (pain, substance use and service use), we will conduct an analysis that examines sex and race/ethnicity as moderators of treatment response. These analyses will be conducted through the inclusion of interaction effects in models so sex and race/ethnicity effects can be formally tested. In light of the differences in substance use, body habitus, and substance metabolism between men and women, we will include a sex interaction term for the analysis of the relationship between self-reported levels of substance use and levels of ETG found in nail clippings. While the use of subgroup analysis might be interesting to look at sex-specific characteristics such as the influence of pregnancy or stage of menstrual cycle, we currently have no relevant covariates making the case for this type of sub-analysis.

Sensitivity Analysis

We anticipate some missingness will occur not completely at random. In general, more sensitive information such as use of illicit substances is less likely to be shared by participants when responding to an interviewer. Based on our previous study (R34), we anticipate there might be a difference in the follow-up rate between Veterans in the two arms of the trial, with veterans in the usual care arm more frequently dropping out. We have created scenarios to minimize missing data through design considerations (i.e., increasing our payment scale as incentive, regular reminder calls), but our analytic plan includes the investigation of missingness. Patterns of missingness will be examined by each individual covariate in the data (univariate, monotone or non-monotone). Chi-squares and t-tests will be run to see if missingness is related to other variables in the analysis (for example: intervention status, substance use). We intend to utilize multiple imputation in the case of variables missing either completely at random or at random. To reduce the likelihood of MNAR, the multiple imputation model will include “auxiliary variables” which are highly correlated with both the variable that has missing data and the probability that the variable is missing. Sensitivity analyses will be conducted as part of the multiple imputation procedure in SAS 9.4 (PROC MI).

Sources of data

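### Unsolicited adverse-event detection has an extra route in SBIRT-PM only, and no source label separates it, so raw counts by arm may be inflated for SBIRT-PM

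*Combined protocol and SAP*

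**What the plan says.** **Solicited detection, same in both arms.** For baseline, week 12 and week 36, Section 7.2 states that "the study team will inquire about the occurrence of AE/SAEs since the last visit". Section 6.2.5 has both follow-up interviews attempted whether or not the counseling was taken up. Sections 3 and 6.2.3 have them done by research assistants blind to arm. PHQ-9 item 9 is asked of everyone at the same visits (Section 7).

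**Unsolicited detection, not the same.** Section 7 says "research staff will be trained in the detection and investigation of adverse events during the conduct of study assessments or other interactions with participants", and Section 7.2 has unanticipated problems recorded when discovered. Section 7 lists as an expected adverse experience "Suicidal ideation detected by the PHQ-9 or by counseling", and suicidality voiced to the SBIRT-PM clinician is evaluated. Section 7.3 counts complaints about the counseling as adverse events, and these cannot arise in usual care.

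**Contact by arm.** SBIRT-PM has an initial session, up to three follow-up calls by week 12, and one more between weeks 12 and 32 (Précis; Section 5.1). Outside the interviews, usual care is described as receiving one contact, in which the Project Director gives the assignment (Section 5.1). Counselors may inform their calls with "information the counselor has obtained from the PACT providers or information in the electronic health record".

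**Use of the data.** Section 7.6 has annual reports that set adverse-event rates against pre-study assumptions. Section 8 allows the study to stop if "the intervention is associated with adverse effects that call into question the safety of the intervention". Section 7.1 is marked not applicable, and Section 9.6 contains no safety analysis.

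**The concern.** When one arm has more occasions on which an event can come to light, its recorded count can exceed the other's at equal true risk. Here the extra occasions come with the intervention, and one of the expected events, suicidal ideation, can be found on them. Higher usual-care dropout would push the same way: Section 9.6 thinks it possible, on the basis of the team's previous study, that follow-up will differ, with "veterans in the usual care arm more frequently dropping out".

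At stake is the reading of safety data by the monitors, by whoever makes the Section 8 judgment, and by readers of the final report. Usual care is the natural reference for all of them. If events are pooled without their source, an excess in SBIRT-PM cannot later be divided into more harm and more looking.

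**Working it through.** The documents state no adverse-event rate, expected count, detection probability or dropout by arm, so there is no planned figure to reproduce. The one usable retention input is the 27% attrition in Section 9.2, and it is internally consistent: 400 / 0.73 = 548 per arm, × 2 = 1096.

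**1. Contacts after randomization.** Usual care: 2 interviews, plus the assignment contact. SBIRT-PM: the same 2 interviews plus up to 1 + 3 + 1 = 5 calls.

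**2. Calls at pilot uptake.** Section 10.3.5 reports that 80% received any counseling, and 55% of those had at least two sessions.
- Lower bound, if everyone with two or more had exactly two: 0.80 × (1 + 0.55) = 1.24 calls per participant.
- Upper bound, if everyone with two or more had five: 0.80 × (0.45 × 1 + 0.55 × 5) = 2.56.

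The average excess is therefore well below five.

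**3. Illustrative detection model, equal true risk in both arms.**
- Usual care: P = R_uc × s
- SBIRT-PM: P = 1 − (1 − R_sb × s) × (1 − 0.80 × c)

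R is the chance of being interviewed, averaging 73% over the arms (Section 9.2). The 0.80 is pilot uptake. Assumed, because the documents are silent: s, the chance that an interviewed participant reports the event (0.6 to 1.0); c, the chance that a counselor picks it up in someone counseled (0 to 0.3); and the retention gap (0 to 15 points, lower in usual care).

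| Retention, usual care / SBIRT-PM | s | c | Detected, usual care | Detected, SBIRT-PM | Ratio |
|---|---|---|---|---|---|
| 73% / 73% | 0.8 | 0 | 0.584 | 0.584 | 1.00 |
| 73% / 73% | 0.8 | 0.1 | 0.584 | 0.617 | 1.06 |
| 73% / 73% | 0.8 | 0.3 | 0.584 | 0.684 | 1.17 |
| 68% / 78% | 0.8 | 0 | 0.544 | 0.624 | 1.15 |
| 68% / 78% | 0.8 | 0.3 | 0.544 | 0.714 | 1.31 |
| 65.5% / 80.5% | 0.6 | 0.3 | 0.393 | 0.607 | 1.54 |

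Fifth row written out: 0.68 × 0.8 = 0.544; 1 − (1 − 0.78 × 0.8) × (1 − 0.80 × 0.3) = 1 − 0.376 × 0.76 = 0.714; 0.714 / 0.544 = 1.31. The whole grid runs from 1.00 to 1.54.

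**4. In counts.** With 550 per arm and an assumed true risk of 10%, the fifth row gives 550 × 0.10 × 0.544 ≈ 30 recorded events in usual care and 550 × 0.10 × 0.714 ≈ 39 in SBIRT-PM, with no true difference.

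**The case against.** The strongest reply is that the plan contains no between-arm safety comparison that could be biased. Section 7.6 compares rates with pre-study assumptions, Section 7.4 sends the IRB overall totals at continuing review, and Section 9.4 says there are no interim analyses or stopping rules. Section 8 asks for effects that cast doubt on safety, not for a difference in counts, and Section 7.4 has each serious event examined for a causal link. Section 7.3 also excludes symptom exacerbations and medication side effects, which narrows what a counselor could add. All of this stands. It limits the consequence to judgment and description, but it does not make the counts comparable.

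Several stronger readings are tempting, and the documents do not support them:
- **A two- to threefold distortion.** A reader might set seven contacts against two and compute 1 − (1 − q)^7 against 1 − (1 − q)^2, which for q from 5% to 20% gives ratios of 3.1 to 2.2. That treats calls with no specified adverse-event inquiry as equal to interviews that make one, lets a contact detect an event that has not yet happened, and gives everyone all five calls.
- **Usual-care participants who miss an interview are never asked.** A missed week 12 can be recovered at week 36, because the person is still contacted and the question reaches back to the last visit. Only those with no later interview are lost, in either arm.
- **Greater usual-care dropout is established.** Section 9.6 says only that it might occur, and gives no size.
- **Counselor chart review is a safety source.** Section 5.1 makes it optional, and its examples concern consults and engagement with services.

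**Conclusion.** The concern holds in a limited form. Solicited detection is equal by design. Unsolicited detection has an additional route in SBIRT-PM, and the plan neither labels it nor sets a common-source count beside it. Raw counts by arm may therefore be inflated for SBIRT-PM. It cannot be said that they are, or by how much.

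The range of 1.00 to 1.54 illustrates the possible size and is not an estimate. It rests on assumed recall, counselor pickup and retention gap, on independence of the two routes, on pilot uptake carrying over, and on any gap running in the direction Section 9.6 anticipates. If counselors pick up little and retention is equal, the distortion is close to nil. Within the grid it is neutral or against SBIRT-PM.

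**What to change.** 1. In Section 7.2, record the detection source of every adverse and serious adverse event: scheduled interview, PHQ-9 item 9, counseling call, counselor chart review, or other.
2. In any by-arm safety summary, whether for the monitoring in Section 7.6, for the Section 8 judgment or in the final report, give events elicited at the blinded week 12 and 36 interviews, including PHQ-9 item 9, as the like-for-like comparison, with the number interviewed in each arm.
3. Show all events in full beside it, labeled by source, including those found only through counseling and complaints about counseling. They should not be dropped: distress from counseling is an expected harm of the intervention, and removing it would tilt the picture toward SBIRT-PM.
4. Optionally, use the VA data already planned for costing in Section 3 ("which includes information on all inpatient and outpatient encounters at VA facilities") as a supplementary check on serious events for all randomized participants. It misses non-VA admissions. It is also not arm-neutral if counseling brings more Veterans into VA care, since Section 5.1 has counselors explain how to obtain eligibility. Death records are not named in that extract and would be a new request.

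Reporting duties for individual events are unchanged. The cost is one log field and one extra table. Section 9.5.1 already gives week 36 nail-return figures, so some events are probably already logged; their source would have to be filled in from existing records where these allow, and marked unknown otherwise.

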7.3 Adverse Events and Serious Adverse Events

An adverse event (AE) is any untoward medical occurrence in a subject during participation in the research study. Veterans with MSD have a high frequency of medical and psychiatric difficulties. Therefore, changes in medication regimen, the presence of medication side effects and symptom exacerbations are not untoward and do not constitute adverse events.

Anticipated adverse events include complaints about the study procedures and the counseling intervention, and any occurrence in which the patient attributes discomfort, harm or disability to the study procedures.

Serious adverse events (SAEs) are adverse events that result in: death, a life-threatening experience, hospitalization, or the need for medical, surgical, behavioral, social or other interventions to prevent such outcomes. Any report that a patient required overnight treatment in any facility (emergency room, detoxification, and hospitalization) will constitute a SAE. Hospitalization or death of another individual due to direct action of patient will also be considered a SAE.

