7.6 Safety Monitoring

A Data and Safety Monitoring Committee (DSMC) will be appointed by NCCIH to review study progress, assess the adequacy of ongoing enrollment & site performance, ensure adequacy of data acquisition & protocol adherence and evaluate overall safety throughout trial implementation. The DSMC will meet at least annually after trial initiation. A DSMC Charter Document outlining the operating guidelines for the committee, the frequency of planned meetings and the specific data presentation format will be agreed upon during the initial meeting of the DSMC. Study reports will be created by the study data center, following a standardized format, as directed by the DSMC. The DSMC will report directly to NCCIH.

Study progress and safety will be reviewed annually during the RCT. Progress reports, including patient recruitment, retention/attrition, and AEs will be provided to the DSMB annually. This Annual Report will include a list and summary of AEs. In addition, the Annual Report will address (1) whether AE rates are consistent with pre-study assumptions; (2) reason for dropouts from the study; (3) whether all participants met entry criteria; (4) whether continuation of the study is justified on the basis that additional data are needed to accomplish the stated objectives of the study; and (5) conditions whereby the study might be terminated prematurely. The Annual Report will be sent to the Independent Monitor(s) and will be forwarded to the VA Central IRB and the NCCIH Program Officer within 1 month of each monitoring review.

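### Section 7.3 leaves an overnight admission for an exacerbation or medication side effect classifiable either way, and drops serious ones without an overnight stay unless the participant attributes them to the study

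*Combined protocol and SAP*

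**What the plan says.** Section 7.3 contains five statements that bear on the point.

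- The general definition: "An adverse event (AE) is any untoward medical occurrence in a subject during participation in the research study".
- The exclusion, justified by how often this population has medical and psychiatric problems: "changes in medication regimen, the presence of medication side effects and symptom exacerbations are not untoward and do not constitute adverse events".
- A list of anticipated AEs, which covers complaints about the study and "any occurrence in which the patient attributes discomfort, harm or disability to the study procedures".
- The SAE definition, which begins "Serious adverse events (SAEs) are adverse events that result in: death, a life-threatening experience, hospitalization" and goes on to include events needing intervention to prevent such outcomes.
- The overnight rule: "Any report that a patient required overnight treatment in any facility (emergency room, detoxification, and hospitalization) will constitute a SAE". A further sentence makes hospitalization or death of another person, caused directly by the participant, an SAE.

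Elsewhere, Section 7 lists "Suicidal ideation detected by the PHQ-9 or by counseling" among the expected adverse experiences and requires any positive answer to PHQ-9 item 9 to be evaluated further. Section 7.1 gives no safety parameters. Under Section 7.2, at baseline, week 12 and week 36 "the study team will inquire about the occurrence of AE/SAEs since the last visit". Sections 7.4 and 10.3.3 send AEs and SAEs to the monitors, the IRB and the funder. The annual report in Section 7.6 must address "whether AE rates are consistent with pre-study assumptions".

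**The concern.** If an SAE must first be an AE, then whatever the exclusion removes from AEs cannot become an SAE, however severe. The overnight rule says the opposite for one class of event. Two staff members could classify the same admission differently and both be following the protocol.

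The definition matters because it decides what is recorded at the three inquiries and therefore what the monitors see. Section 9.4 plans no interim analysis and no stopping rules, and Section 7.6 describes the progress reports as recruitment, retention and AEs. The AE and SAE summaries are thus the main safety information the monitors are described as receiving during the trial. The intervention encourages people with chronic pain to take up new pain care, so a pain flare is a harm it could plausibly cause, and a pain flare is a symptom exacerbation.

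**Working it through.** No figure is in dispute and no arithmetic applies. The check takes each kind of event through the sentences of Section 7.3 in turn.

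| Event | Exclusion plus SAE-as-subset-of-AE | Overnight rule | Attribution clause | Result |
|---|---|---|---|---|
| Exacerbation or medication side effect with overnight treatment, not attributed to the study | Not an AE, so not an SAE | SAE | Does not apply | Either answer is open |
| Exacerbation or medication side effect that is serious on another criterion (for example, same-day intervention that averts admission), not attributed | Not an AE, so not an SAE | Does not apply | Does not apply | Excluded |
| Exacerbation or medication side effect that the participant attributes to study procedures | Excluded by the general phrase | Depends on stay | AE | Counted, if the specific clause governs |
| Non-serious exacerbation or medication side effect, not attributed | Not an AE | Does not apply | Does not apply | Excluded, which appears intended |
| Overnight detoxification | Detoxification and withdrawal are not named in the exclusion | SAE, named expressly | Not needed | Counted |

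**First row.** The outcome depends on which sentence the classifier treats as governing, and no section says.

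**Second row.** This does not depend on that choice. Even if the overnight rule is read as overriding the exclusion, there is no overnight stay for it to act on, and the base SAE definition still requires an AE. The only way back in is the attribution clause. That clause covers attribution by the participant, not by staff, and only to study procedures. Under Section 5.1 the counselors motivate and refer, and other providers place the consults. A participant may well attribute a flare to the referred treatment rather than to the study.

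**Suicidal ideation.** Section 7 names it as an expected adverse experience and sets out how it is evaluated. Section 7.3 does not name it among the anticipated AEs and excludes symptom exacerbations in general. Identification and evaluation are therefore covered. What is unstated is whether new or worsened ideation is entered as an AE.

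**Other measurements.** Section 6.1 schedules the BPI, PHQ-9, ASSIST and opioid dispensing at all three assessments in both arms. Deterioration can be seen there at final analysis, but no section sends those results by arm to the monitors as the trial proceeds.

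**The case against.** The best defense is that the SAE paragraph gives a base definition followed by two extensions. The overnight sentence is unconditional. The sentence after it makes harm to a third person an SAE, and such harm cannot be a medical occurrence in the participant. So the paragraph does not hold strictly to the rule that every SAE is first an AE, and on this reading admitted exacerbations are SAEs. This is plausible and may be what was meant, but the text does not say it, and it leaves the second row of the table unchanged.

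It is also fair to say that leaving out background fluctuation is a reasoned choice in a minimal-risk telephone-counseling trial. That stands for non-serious events. It does not justify an exclusion with no limit by seriousness.

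Several stronger readings are tempting, and the documents do not support them.

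- A reader might infer that withdrawal and all side effects of newly started treatment are removed. The exclusion covers only medication side effects, whereas SBIRT-PM promotes non-pharmacological care. Withdrawal is not listed, and overnight detoxification is expressly an SAE.
- A reader might infer that participant-attributed harms are lost, or that suicidal ideation is ignored. Specific text in Sections 7.3 and 7 covers both.
- A reader might infer that the excluded classes are the most common serious events. No event rate is given, and the overnight rule, if applied, captures admissions.
- A reader might infer that early stopping turns on these counts. The first ground in Section 8 refers to adverse effects in general, without a threshold or a named count.

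**Conclusion.** The concern holds in a limited form. Section 7.3 gives two answers for an overnight admission caused by an exacerbation or medication side effect. It excludes the same kind of event when it is serious on another criterion, involves no overnight stay and is not attributed by the participant to study procedures. The AE and SAE counts that go to the monitors are therefore ambiguous and can omit serious events, and any between-arm safety table built on them inherits the problem.

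The size cannot be stated as a number, because the documents give no rate for these events. The conclusion rests on the wording alone and assumes that no operating document outside the protocol settles precedence. It would be too strong to say that plausible harms in general go uncounted, since overnight events count if staff let that sentence govern and participant-attributed events are AEs. Sample size, primary outcomes and efficacy analyses are unaffected. Severity is moderate: worth correcting before safety results are reported, but not a flaw that undermines the trial.

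**What to change.** Reconcile the sentences of Section 7.3 with each other and with the Section 7 listing:

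1. State that the exclusion does not apply to any event that meets an SAE criterion, or that the participant or staff attribute to the study. It then covers only non-serious fluctuation of pre-existing conditions.
2. State whether new or worsened suicidal ideation is recorded as an AE.
3. Re-classify the events already logged, and the PHQ-9 item 9 records, under the reconciled rule. Section 9.5.1 already reports week-36 nail-return rates, so follow-up is well advanced and new wording alone would change little.
4. Use the VA encounter data already planned for costing (Section 3, Costs Estimation Procedures) to identify VA admissions in both arms. The log cannot show events that were never entered.
5. Report the limits of this recovery: events never recorded anywhere, and care outside VA, may not be retrievable.

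The cost is a wording change, somewhat more events to report, and a modest data check.
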